## 8. Data management and statistics

### 8.1. Data management

Each patient who signs a consent form to participate in the study will be assigned a unique identification number (i.e. patient screening number) for identification purposes. Each patient should be assigned only one number. Should the patient fail to qualify for the study, his/her identification (screening) number must not be re-used for any other patient in the study.

CRF and paper documents provided to the patient (i.e. diary and AE reporting form) will include the unique patient identification (screening) number in the header.

The collected data will be included in the following source documents: patient's case report form (CRF) and diary. These completed documents will be provided by the investigator to the sponsor. In practice, the investigator records these completed documents in an appropriate binder and sends the scan of the documents by email to the sponsor. Tracking of completed source documents is performed: when a patient completed the clinical investigation but the related source documents have not been received, an email is sent to the investigator/study coordinator to request missing documents.

Duration, intensity and/or interruption of the treatment are recorded for each patient thanks to a built-in electronic system in the device. Each device will bear a unique randomization number that has to be reported in the patient's CRF and will allow to identify which device was used by each patient.

In case of lack of data accuracy (missing data, unclear data, discrepancies), a Data Clarification Form is sent to the investigator. The completed and signed form is sent back to the sponsor. Tracking of Data Clarification forms is performed to ensure that all Data Clarification forms are completed by the investigator/study coordinator.

AE and SAE are collected and investigators will report SAE and AE to the sponsor using the specific collecting forms annexed to the CRF. These SAE and AE collecting forms will be reviewed and analysed by the sponsor when received. The device defects are also collected and investigators will report device defects to the sponsor using the CRF.

### 8.2. Statistics

The statistical analysis of the data obtained from this study will be the responsibility of the sponsor.

#### 8.2.1. Sample size

The sample size was computed based on the primary outcome, i.e. pain freedom at 2 hours. The sample size should allow detecting a statistically significant difference between the treatment (verum) and control (sham) outcome value with a power of at least 90% and a 5% level of significance.

In the pilot clinical trial, the pain freedom at 2 hours associated with the Cefaly® Abortive Program treatment was 35.4%. Results from previous randomized, sham-controlled trial using a stimulation device (transcranial magnetic stimulator) as acute treatment of migraine reported 22.0% of pain freedom at 2 hours in the sham group (11).

A power analysis showed that a sample of 239 patients per group allows detecting a statistically significant difference between the treatment (35.4%) and control (22.0%) pain freedom at 2 hours with a power of at least 90% and a 5% level of significance.

Taking into account a rate of 20% of patient loss during the study (based on the pilot clinical trial), at least 299 patients should be included in each group. Consequently, 600 patients will be included in the present clinical investigation.

NOTE: The sample size meets the FDA definition of Phase III clinical investigation (according to the FDA, a clinical investigation can be considered as a Phase III clinical study when the number of participants ranges from 300 to 3,000 volunteers who have the disease or condition).

#### 8.2.2. Study hypotheses

The general hypothesis is that the Cefaly® Abortive Program device is safe and effective for the abortive treatment of migraine.

In particular, for the abortive treatment of migraine:

- 2 hours of e-TNS with the Cefaly® Abortive Program device is better than 2 hours of sham e-TNS to achieve pain freedom, as measured by the pain freedom at 2 hours and the sustained pain freedom at 24 hours.
- 2 hours of e-TNS with the Cefaly® Abortive Program device is better than 2 hours of sham e-TNS to achieve symptoms freedom, as measured by the MBS freedom at 2 hours and the absence of migraine-associated symptoms at 2 hours.
- 2 hours of e-TNS with the Cefaly® Abortive Program device is better than 2 hours of sham e-TNS to achieve pain relief, as measured by the pain relief at 2 hours and the sustained pain relief at 24 hours.
- Anti-migraine rescue medication intake is lower after 2 hours of e-TNS with the Cefaly® Abortive Program device than after 2 hours of sham e-TNS.
- No serious adverse events (SAE) due to the 2-hour e-TNS session with the Cefaly® Abortive Program device within the 24 hours following the beginning of the treatment.

### 8.2.3. Statistical methods

- All relevant general, safety and efficacy data will be descriptively summarized at each time point.
- Continuous data will be summarized by the number of subjects (N), the arithmetic mean, the standard deviation, the coefficient of variation as a percentage (CV%), the median, the inter-quartile range, the minimum and the maximum value, when appropriate.
- Categorical data will be summarized by absolute (N) and relative (%) frequency tables.
- Where considered as relevant, the study data will also be graphically depicted.
- For each patient, the outcomes will be calculated according to all data available, and if necessary, imputation of missing data will be performed according to the last value carried forward method.
- Unless otherwise stated, all statistical tests will be conducted at the  $\alpha=0.05$  (2-sided) level.
- Comparison between two independent samples (verum and sham group) will be performed using either the Mann-Whitney U test (also called the Mann-Whitney-Wilcoxon (MWW), Wilcoxon rank-sum test, or Wilcoxon-Mann-Whitney test), the Fisher test or the Anova test.

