##### Secondary outcomes:

1. Pain Relief (PR) at 2 hours, defined as the percentage of patients having a reduction of a moderate or severe migraine headache (Grade 2 or 3) at baseline to a mild headache or to no headache (Grade 1 or 0) at 2 hours after the beginning of the e-TNS session.
2. Percentage of patients with absence of photophobia, phonophobia, nausea, vomiting at 2 hours after the beginning of the e-TNS session.
3. Use of rescue medication between 2 and 24 hours, defined as the percentage of patients who took anti-migraine rescue medication between 2 and 24 hours after the beginning of the e-TNS session.
4. Sustained pain freedom at 24 hours, defined as the percentage of patients having no headache (Grade 0) at 2 hours, with no use of anti-migraine rescue medication and no relapse of headache pain within the 24 hours after the beginning of the e-TNS session.
5. Sustained pain relief at 24 hours, defined as the percentage of patients having mild or no headache (Grade 1 or 0) at 2 hours, with no use of anti-migraine rescue medication and no relapse of headache pain within the 24 hours after the beginning of the e-TNS session.

Note: The baseline corresponds to the beginning of the e-TNS session.

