#### 4.2.3. Post-treatment phase

Starting two hours after the beginning of the treatment session, the patient is allowed to take anti-migraine rescue medication if and only if the migraine headache pain is moderate or severe, either because there has not been pain relief or because after initial pain relief (no headache or mild headache pain) a moderate or severe headache is resuming.

The patient will have to report the following data in his/her diary at 24 hours after the beginning of the treatment session (24-hour data):

- the rescue medication intake, if any, between 2 hours and 24 hours after the beginning of the treatment session, and, if applicable, the time when the medication was taken
- the headache pain severity on the following scale: 0 = no pain; 1 = mild pain; 2 = moderate pain; 3 = severe pain

- the migraine-associated symptoms (photophobia, phonophobia, nausea, vomiting)

In his/her AE reporting form, the patient will record any adverse event occurring during the 24 hours following the beginning of the treatment session and is instructed to notify the investigator immediately for any serious adverse event with the stimulation.

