#### 4.2.4. Final visit

The patient will be instructed to return to the investigation site within approximately 4 days after the treatment session to return the study material, i.e. the Cefaly® Abortive Program device as well as completed paper diary and AE reporting form. The investigator will review the diary in details to ensure data completeness and accuracy (to avoid any missing data, unclear data or discrepancies). If necessary, the investigator will instruct the patient to make him/herself corrections and to sign the corrections with his/her identification (screening) number and the date (no initials).

All adverse events reported on the AE reporting form will be reviewed by the investigator to assess severity. The investigator will also ask the patient if he/she has experienced any adverse effects not reported on the form. Additionally, the investigator will ask the patient if he/she has experienced any device defects.

If a patient has not treated a migraine attack within two months following the screening visit, the study material (Cefaly® Abortive Program device with accessories) will have to be returned to the study site. This will be considered as a protocol violation.

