### 8.2.4. Statistical analysis

#### Efficacy analysis

The efficacy analysis will be executed on a modified intention-to-treat (mITT) basis.

Patient data will be included in the mITT analysis if all the four following conditions are met:

1. The patient treated a qualifying migraine.
2. The patient applied the Cefaly® Abortive Program treatment (verum or sham) during at least 30 minutes\*.
3. The headache pain severity score **AND** the migraine-associated symptom(s) at baseline were reported in the diary.
4. The headache pain severity score **OR** the migraine-associated symptom(s) at 2 hours were reported in the diary.

\*If the patient stopped the 2-hour treatment session after 30 minutes but before its end for any reason, he/she is kept in the modified intention-to-treat (mITT) analysis if all the other conditions are met.

If the patient takes anti-migraine rescue medication between 2 hours and 24 hours after the beginning of the e-TNS treatment session, the headache pain intensity and migraine-associated symptoms presence

can be affected by the medication and the last value carried forward method (2-hour value carried forward method in this case) will be applied for the 24-hour time point headache pain severity and migraine-associated symptoms.

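### Last value carried forward lets a 2-hour responder with a blank 24-hour pain grade count as sustained without being observed, which biases the sustained pain freedom and sustained pain relief rates upward in each arm

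*Combined protocol and SAP*

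**What the plan says.** Section 3.1 defines secondary outcomes 4 and 5 (sustained pain freedom and sustained pain relief at 24 hours) as a 2-hour response together with "no use of anti-migraine rescue medication and no relapse of headache pain within the 24 hours after the beginning of the e-TNS session".

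For missing data, section 8.2.3 gives one general rule: "if necessary, imputation of missing data will be performed according to the last value carried forward method". It names no outcome to which the rule does not apply.

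The mITT conditions in section 8.2.4 require baseline data and one 2-hour item; the last of them is met if the pain score or "the migraine-associated symptom(s) at 2 hours were reported in the diary". Nothing at 24 hours is required.

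The table in section 7.1 places pain severity at baseline, 2 hours and 24 hours only. Rescue intake is collected only with the 24-hour data: section 4.2.3 lists there "the rescue medication intake, if any, between 2 hours and 24 hours after the beginning of the treatment session".

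Section 8.2.4 has a separate rule for patients known to have taken rescue medication: "2-hour value carried forward method in this case) will be applied for the 24-hour time point headache pain severity". It does not cover patients whose 24-hour report is missing.

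**The concern.** Carry-forward supplies the answer that the sustained outcomes are meant to observe. A patient at Grade 0 at 2 hours with no 24-hour grade is assigned Grade 0 at 24 hours; a patient at Grade 1 is assigned Grade 1. Neither can show a relapse, so for that patient the 24-hour pain condition reduces to the 2-hour response.

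At 2 hours the same method is conservative: a missing 2-hour pain grade takes the baseline grade, which is 2 or 3 in a qualifying attack, and the patient fails. At 24 hours it favours success for anyone who had responded at 2 hours.

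Section 8.2.2 uses sustained freedom and sustained relief as measures for the pain freedom and pain relief hypotheses. They are the trial's evidence that the effect lasts, and unobserved successes weaken it.

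**Working it through.** **Inputs from the documents.** Section 8.2.1: 2-hour pain freedom 35.4% on verum and 22.0% on sham. Section 1 (home-treatment pilot): 2-hour pain relief 70.8%, sustained pain freedom 25%, sustained pain relief 50%.

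**The plan's own figure.** The plan states no expected rate or power for outcomes 4 and 5. The inputs borrowed from its sample size are sound: 35.4% v 22.0%, two-sided 5% and 90% power give 238 per group without continuity correction, against the stated 239 (power at 239 is 90.2%), and 239/0.80 gives 299.

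**Retention among 2-hour responders.** r = 25/35.4 = 70.6% for freedom and 50/70.8 = 70.6% for relief. About 29.4% of pilot responders were not sustained.

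**Assumptions, because the documents are silent.** A share m of 2-hour responders has no 24-hour grade and is scored as having taken no rescue. In the base case m is equal in both arms and sham retention also equals 70.6%.

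**Formulas**, with p the 2-hour rate:
- true sustained rate: p × r
- carried forward, missing at random: p × [r + m(1 − r)]
- carried forward, all missing responders are relapsers: p × (r + m)
- missing counted as not sustained, missing at random: p × r × (1 − m)

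**Sustained pain freedom**

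| Rule | m | Verum | Sham | Difference (points) |
|---|---|---|---|---|
| True | – | 25.0% | 15.5% | 9.5 |
| Carried forward, random | 10% | 26.0% | 16.2% | 9.9 |
| Carried forward, random | 20% | 27.1% | 16.8% | 10.3 |
| Carried forward, relapsers missing | 10% | 28.5% | 17.7% | 10.8 |
| Carried forward, relapsers missing | 20% | 32.1% | 19.9% | 12.1 |
| Not sustained, random | 10% | 22.5% | 14.0% | 8.5 |
| Not sustained, random | 20% | 20.0% | 12.4% | 7.6 |

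If the missing responders are all relapsers, counting them as not sustained returns the true rate p × r.

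**Sustained pain relief, verum** (true 50.0%). Random: 50.0 + m × (70.8 − 50.0) gives 52.1% at m = 10% and 54.2% at 20%. Relapsers missing: 50.0 + m × 70.8 gives 57.1% and 64.2%.

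**In patients.** With 239 per arm and m = 10%, 239 × 0.354 × 0.10 = 8.5 verum and 239 × 0.22 × 0.10 = 5.3 sham responders would be credited unobserved. At 29.4% non-retention, about 2.5 and 1.5 of them would be false successes.

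**Direction of the difference.** With equal random missingness, carry-forward changes it by m × [pV(1 − rV) − pS(1 − rS)]. The verum term is 0.354 − 0.250 = 0.104. The change is zero when 0.22 × (1 − rS) = 0.104, that is rS = 52.7%; below that the difference shrinks. At rS = 50% and m = 20% it goes from 14.0 to 13.9 points. With equal 70.6% retention but m = 5% on verum and 20% on sham, carry-forward gives 25.5 − 16.8 = 8.7 points against a true 9.5; with m = 20% on verum and 5% on sham it gives 11.2.

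**The case against.** **Rescue status is missing too.** A patient who returns no 24-hour report has no rescue entry either, and there is no earlier 2-to-24-hour value to carry. A reader might infer that the plan expressly scores such a patient as sustained. It does not: it has no rule for absent rescue data. The result follows from the text only when the grade is blank and rescue is recorded as not taken. For a wholly missing report it is the likely reading, because nothing recorded would be taken as no rescue, but it is inferred. This stands, and the fix must cover rescue status.

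**The difference need not widen.** A reader might infer that the rule favours verum because more verum responders are expected. That holds under equal retention and equal missingness, but the documents give neither sham retention nor missingness by arm, and the working shows reversals. This stands.

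**Missingness may be low.** At the final visit, "The investigator will review the diary in details to ensure data completeness and accuracy", and section 8.1 adds Data Clarification Forms. The 20% loss in section 8.2.1 is patient loss over the whole study, not a rate of missing 24-hour reports among mITT responders. The largest figure, 12.1 points, needs 20/29.4 = 68% of relapsers to be missing and no one else. This limits the size; it does not change how the remaining gaps are scored.

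**The remedy has its own bias.** Under random missingness, counting missing as failure lies further from the truth than carry-forward: at m = 10%, 22.5% against a true 25.0%, compared with 26.0%. This also stands. The case for the remedy is that it errs against the claim of durability and credits no unobserved success.

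**Conclusion.** The concern holds for secondary outcomes 4 and 5. As written, the rule credits 2-hour responders who have no 24-hour grade with sustained response, provided no rescue is recorded. Whenever some of those patients would have relapsed, each arm's sustained rate is too high: by about 1 point for verum sustained freedom at 10% random missingness and 2 points at 20%, and by more if relapsers are the ones who do not report. These sizes assume that the pilot's 70.6% retention carries over and that m lies in the range shown; the documents do not give m.

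No direction can be claimed for the verum-sham difference. Nor does the rule turn missing data in general into success: 2-hour non-responders fail whatever is missing later, and a missing 2-hour pain grade carried from baseline fails the sustained outcomes as well. The carry-forward for known rescue users in section 8.2.4 creates no sustained successes, since recorded rescue already fails the definition. The 2-hour primary outcomes and the sample size are untouched. The change should be made, but the trial's main conclusion does not depend on it.

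**What to change.** State in section 8.2.3 that last value carried forward is not used to meet the 24-hour conditions of outcomes 4 and 5. In the main analysis, count an mITT patient with a missing 24-hour pain grade, or with missing rescue status for 2 to 24 hours, as not sustained; a recorded relapse or recorded rescue use fails already. Report the number missing per arm, for pain grade and for rescue status. Give the carried-forward and observed-case versions as sensitivity analyses.

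The cost is a short addition to the text and one table. The main sustained rates become conservative under random missingness. They are also sensitive to unequal missingness: with m = 20% on verum and 5% on sham, and equal retention, the sustained freedom difference would be 20.0 − 14.8 = 5.2 points against a true 9.5. The per-arm counts and the sensitivity analyses make this visible.

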Nevertheless, these safety and efficacy evidences were mainly reported for migraine patients treated in the clinic and for migraine lasting already for several hours. In order to get data with identical protocol design as usually carried out for abortive migraine medication triptans (i.e. treatment at home, on a migraine attack at an early stage of its development), a pilot trial has been implemented by [name] at Rochester Clinical Research, Inc., Rochester, New York, USA (10). The efficacy outcomes were very encouraging: 35.4% of patients were pain-free at 2 hours and 60.4% free from their most bothersome migraine-associated symptom, 70.8% had pain relief at 2 hours, sustained pain freedom and sustained pain relief at 24 hours were respectively 25% and 50%.

Consequently, there are enough evidences, pilot and Phase II data, to go for a Phase III multicenter, randomized, double-blind, sham-controlled trial on the acute treatment of migraine at home with e-TNS using a Cefaly® Abortive Program device.

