## 2. Study objective

The main objective of this study is to have Phase III evidences of the efficacy of the Cefaly® Abortive Program device used at home for 2 hours to treat a migraine attack, as triptans are generally used. That is to say having randomized, double-blind, sham-controlled data of the efficacy and safety of the Cefaly® Abortive Program device in the abortive treatment of acute migraine as measured by 2-hour pain freedom, pain relief and migraine-associated symptoms freedom, plus evolution of these measurements for 24 hours after the beginning of the treatment session.

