### 3. Study outcomes

#### 3.1. Efficacy outcomes

##### Primary outcomes:

1. Pain Freedom (PF) at 2 hours, defined as the percentage of patients having a reduction of a moderate or severe migraine headache (Grade 2 or 3) at baseline to no headache (Grade 0) at 2 hours after the beginning of the e-TNS session.
2. Most bothersome migraine-associated symptom (MBS) freedom at 2 hours, defined as the percentage of patients with absence, at 2 hours after the beginning of the e-TNS session, of the most bothersome migraine-associated symptom identified at baseline.

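### The plan names two primary outcomes, sizes on one, tests each at two-sided 0.05, and gives no rule that turns the two results into a trial conclusion.

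*Combined protocol and SAP*

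**What the plan says.** Section 3.1, under the plural heading for primary outcomes, numbers two. The first begins "Pain Freedom (PF) at 2 hours, defined as the percentage of patients having a reduction of a moderate or severe migraine headache". The second begins "Most bothersome migraine-associated symptom (MBS) freedom at 2 hours, defined as the percentage of patients with absence".

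Section 8.2.1 uses the singular: "The sample size was computed based on the primary outcome, i.e. pain freedom at 2 hours". Its power of at least 90% and its 5% level are attached to that one comparison, 35.4% against 22.0%, giving 239 per group, 299 after 20% loss, and 600 in total.

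Section 8.2.2 puts pain freedom and MBS freedom in separate hypotheses, each paired with secondary measures. The symptom hypothesis is to be judged "as measured by the MBS freedom at 2 hours and the absence of migraine-associated symptoms at 2 hours". No success criterion is attached.

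Section 8.2.3 sets the level: "Unless otherwise stated, all statistical tests will be conducted at the" two-sided 0.05 level. Nothing is stated otherwise for either primary outcome. Section 8.2.4 defines the modified intention-to-treat set, the 24-hour carry-forward rule and the safety analysis, and is silent on combining the two primaries.

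**The concern.** With two primary outcomes the results can split. If one is significant and the other is not, the plan does not say whether the trial has succeeded. Each outcome has its own full 0.05, so a sponsor following the text could claim success on whichever one wins.

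The rule decides which planning figure carries over to the trial. If either outcome suffices, the trial's error exceeds 5%. If both must succeed, the 5% holds but the 90% for pain freedom becomes only a ceiling on the trial's power. If pain freedom is tested first and MBS freedom follows only on success, the 5% holds and the 90% stands for the first test. A rule chosen after unblinding could not be shown to control error. This matters in a trial described as Phase III whose analysis is the sponsor's own responsibility.

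**Working it through.** **Inputs.** From 8.2.1: pain freedom 35.4% (verum) and 22.0% (sham), 5% level, power at least 90%, 239 per group, 20% loss. From 8.2.3: two-sided 0.05 per test. From section 1, the pilot: "35.4% of patients were pain-free at 2 hours and 60.4% free from their most bothersome migraine-associated symptom". Assumed, because the documents do not give them: a sham MBS rate of 40%, 45% or 50%, and the correlation r between the two outcomes.

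**1. The plan's own figure.** Pooled two-proportion formula, mean rate (0.354 + 0.220)/2 = 0.287:

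n = [1.960·√(2·0.287·0.713) + 1.282·√(0.354·0.646 + 0.220·0.780)]² / 0.134² = 237.4, so 238 per group.

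At 239 the power is 90.2%. The stated 239 is reproduced to within one patient. 239/0.80 gives 299. With 600 randomized and 20% lost, 600·0.80/2 = 240 per arm remain, where power is 90.3%.

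**2. Attainable correlation.** For two binary outcomes with rates p < q, r is at most √[p(1−q)/((1−p)q)].
- Sham, 22% with 40%, 45% or 50%: 0.65, 0.59 or 0.53.
- Verum, 35.4% with 60.4%: 0.60.

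So r runs from 0 to about 0.65 at most.

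**3. Either suffices, both nulls true.** At r = 0 the two-sided error is 1 − 0.95² = 9.75%, and the error favouring verum is 1 − 0.975² = 4.9%. Other values of r use the bivariate normal.

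| r | two-sided (against 5%) | favouring verum (against 2.5%) |
|---|---|---|
| 0 | 9.75% | 4.9% |
| 0.5 | 9.1% | 4.5% |
| 0.65 | 8.6% | 4.3% |

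**4. Both required.** A false claim needs a false result on at least one true null tested at 0.05, so the 5% holds. Joint power is the bivariate normal probability that both tests succeed. At 240 per arm it reaches 90% only if MBS power is at least 99.7% (r = 0) or 99.1% (r = 0.6). With 60.4% on verum:

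| assumed sham MBS rate | MBS power | joint power, r = 0 to 0.6 |
|---|---|---|
| 40% | 99.5% | about 90% |
| 45% | 92.5% | 83–86% |
| 50% | 63.0% | 57–61% |

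At r = 0 these are products, for example 0.903 × 0.925 = 0.835. In the 50% row the sham limit on r is 0.53, so 61% is an upper limit.

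**5. Fixed sequence, pain freedom first.** MBS freedom can be claimed only after pain freedom is significant, so the error for the two primaries stays at 5% and the 90% stays valid for the first test. The chance of also claiming MBS freedom equals the joint power in step 4.

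**6. Sensitivity to the test.** Fisher's exact test, one of those named in 8.2.3, is conservative here (actual size about 3.9% at 240 per arm). With it, pain freedom power at 239 is 88.5%, the either-suffices error at r = 0 is 7.6%, and joint power at r = 0 is about 88% (sham 40%) or 81% (sham 45%). The conclusion does not change.

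**The case against.** The strongest reply is that 8.2.1 ties the 5% and 90% to pain freedom and never presents them as trial-level figures, so no stated number is wrong. That stands. A reader might infer that the trial's alpha is inflated, that it is underpowered, or that the sample size is miscalculated. The documents support none of these. Inflation arises only if either outcome suffices, a rule the plan does not state; a shortfall below 90% arises only if both are required, and then depends on an unstated sham MBS rate.

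A second reply is that the singular in 8.2.1, and pain freedom's first place in 3.1, point to pain freedom as the lead outcome. They lean that way, and sizing on one of two primaries is possible. The singular may also be loose wording rather than a second design. But neither place gives MBS freedom a lower rank or makes its test conditional, and 3.1 still calls it primary.

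Third, the outcomes come from the same patient, attack and time point, so r = 0 is unlikely. This is fair, but at the highest attainable correlation the either-suffices error is still 8.6%.

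Fourth, the study objective might be cited as further evidence of competing primaries. It is not good support: section 2 speaks of results "as measured by 2-hour pain freedom, pain relief and migraine-associated symptoms freedom", which does not name MBS freedom and fits the secondary symptom outcome at least as well. The point rests on 3.1, 8.2.1 and 8.2.3.

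**Conclusion.** The point holds as a missing decision rule. Sections 3.1 and 8.2.1 need reconciling on the number of primary outcomes, and nothing in the plan says how two primaries, each tested at two-sided 0.05, yield one conclusion. That gap in the text needs no assumption.

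Its size depends on the rule chosen: an error of 8.6% to 9.75% instead of 5% if either suffices (4.3% to 4.9% instead of 2.5% favouring verum), or joint power anywhere from about 57% to about 90% if both are required. The error range rests on r between 0 and 0.65. The power range rests on the pilot's 60.4%, 240 analysed per arm, and assumed sham MBS rates of 40% to 50%. It should be settled before unblinding.

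**What to change.** Make 3.1 and 8.2.1 agree on how many primary outcomes there are, and state the rule in 8.2.3. Recommended: test 2-hour pain freedom at two-sided 0.05, then 2-hour MBS freedom at two-sided 0.05 only if pain freedom is significant. In 8.2.1, say that the 90% applies to the pain freedom test, and preferably add the chance of also claiming MBS freedom under a stated sham rate.

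The cost is two sentences in 8.2.3 and one or two in 8.2.1, with the 600 patients unchanged. The downside is no confirmatory MBS claim if pain freedom fails.

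Other rules are valid if stated in advance. If both must succeed, say so and replace the 90% with joint power under a stated sham MBS rate. A split of 0.025 to each also controls error, but pain freedom power at 239 drops to 84.3%; restoring 90% would take 281 per group, or 281/0.80 = 352 after loss.

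### The five secondary outcomes are written as study hypotheses and each tested at two-sided 0.05 with no gate on the primaries and no adjustment, so one can be declared shown even if the primary analysis fails

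*Combined protocol and SAP*

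**What the plan says.** Section 3.1 names two primary outcomes (pain freedom and freedom from the most bothersome symptom, both at 2 hours) and five secondary outcomes: pain relief at 2 hours, symptom absence at 2 hours, rescue medication between 2 and 24 hours, sustained pain freedom and sustained pain relief. The second of these reads "Percentage of patients with absence of photophobia, phonophobia, nausea, vomiting at 2 hours after the beginning of the e-TNS session". It does not say whether this is one composite comparison or one comparison per symptom.

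Section 8.2.2 places all five secondaries among the study hypotheses, under a general hypothesis of safety and effectiveness. Each has a direction; for example, "Anti-migraine rescue medication intake is lower after 2 hours of e-TNS with the" active device than after sham. Two bullets pair a primary with a secondary: pain freedom with sustained pain freedom, and most-bothersome-symptom freedom with symptom absence. The bullets on pain relief and on rescue medication rest on secondaries alone. Section 2 likewise includes pain relief in the main objective.

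Section 8.2.3 then gives the general rule: "Unless otherwise stated, all statistical tests will be conducted at the" 0.05 level, two-sided. No exception follows. Section 8.2.4 covers the analysis population and carried-forward values, but not the order or status of the tests.

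Section 8.2.1 sizes the trial on pain freedom only, "with a power of at least 90% and a 5% level of significance".

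**The concern.** The trial is presented as Phase III evidence of efficacy. A reader who applies the plan literally would take any secondary with p below 0.05 as support for its hypothesis, whatever happened to the primaries and however many other secondaries were tested. For pain relief and rescue medication, the hypothesis contains no primary at all. The usual answer is that secondary outcomes are understood to be supportive. That answer is weaker here, because the plan writes them as hypotheses and never calls them descriptive or exploratory.

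The efficacy statements drawn from the secondaries are at stake. The primary analysis is not affected.

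**Working it through.** **1. The plan's own figure.** The inputs from 8.2.1 are: "the pain freedom at 2 hours associated with the Cefaly® Abortive Program treatment was 35.4"%; a previous sham-controlled trial that "reported 22.0% of pain freedom at 2 hours in the sham group"; two-sided 5%; and 90% power. With the pooled formula without continuity correction,

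n = [1.960·√(2·0.287·0.713) + 1.282·√(0.354·0.646 + 0.220·0.780)]² / 0.134² = 237.4, so 238 per group.

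The plan states 239, which has 90.2% power by the same formula. Allowing for 20% loss, 239/0.8 = 298.75, so 299, as stated. The sample size reproduces to within one patient per group. It concerns one primary outcome at 0.05, and the documents give no error rate for the secondary family.

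**2. Number of tests.** Pain relief, rescue use, sustained freedom and sustained relief make four. Symptom absence adds one as a composite (k = 5) or four if each symptom is tested (k = 8).

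**3. Independent tests, all secondary nulls true.** The chance of at least one p < 0.05 is 1 − 0.95^k:
- k = 5: 22.6%
- k = 8: 33.7%

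**4. Correlated tests.** The documents give no correlations, so a range is assumed. The results below come from equicorrelated normal test statistics, with 1,000,000 simulated trials per cell.

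| Correlation | k = 5, either direction | k = 8, either direction | k = 5, benefit only | k = 8, benefit only |
|---|---|---|---|---|
| 0 | 22.6% | 33.7% | 11.9% | 18.3% |
| 0.3 | 20.9% | 30.1% | 10.5% | 15.1% |
| 0.5 | 18.3% | 25.1% | 9.1% | 12.5% |
| 0.7 | 14.9% | 19.1% | 7.4% | 9.5% |
| 0.9 | 10.2% | 11.9% | 5.1% | 5.9% |

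The either-direction columns compare with 5% for one test, and the benefit-only columns with 2.5%.

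**5. A check with nested binary outcomes.** By the definitions in 3.1, sustained freedom lies within sustained relief, which lies within 2-hour relief, and rescue use disqualifies a patient from both sustained outcomes. A patient-level null simulation built this in, with 239 per arm and 8,000 runs. Its event rates were assumed (60% pain relief, 28% pain freedom, and 50%, 55%, 75% and 95% symptom absence), as was a shared-factor correlation of 0.3 or 0.6. The chance of at least one p < 0.05 in either direction was:
- Fisher's test, which 8.2.3 lists: 13–15% for k = 5 and 21–23% for k = 8
- uncorrected two-proportion test: 16–19% for k = 5 and 26–29% for k = 8

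The excess over the single-test level therefore survives both nesting and a conservative test.

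**The case against.** The strongest reply is that the plan separates primary from secondary outcomes, sizes the trial on a primary, and nowhere says that a secondary result alone establishes efficacy. Two of the bullets in 8.2.2 join a primary and a secondary with *and*. Read as a conjunction, those two hypotheses also need their primary. This stands as a fair reading, but the text does not settle it, and it leaves pain relief and rescue medication without any primary.

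Four objections to the size of the problem also stand:
- The percentages assume that every secondary null is true.
- Since the hypotheses are directional, the benefit-only figures measure the harm better than the either-direction figures. They are about half as large, but so is their single-test comparator, so the relative inflation is about the same.
- The 34% needs eight independent tests, which nested outcomes cannot be. Nor is 15% a floor, since five tests at correlation 0.9 give about 10%.
- Eight is a possible count, not a stated one.

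A reader might go further and infer that the plan replaces a promised 5% with 15–34%. The documents do not support this: 0.05 is a level per test, and no family-wise rate for the secondaries is promised. A reader might also infer that a lone significant secondary would be reported as confirmed. The plan permits that but does not say it. The background section does cite individual secondary results of an earlier sham-controlled trial as efficacy evidence, but that trial's primary outcome was itself reported as significant. It is no precedent for claiming a secondary after a failed primary.

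**Conclusion.** The gap is real: the inferential status of the secondaries is undefined, and the one rule given lets any of them be declared shown at 0.05 regardless of the primaries. With all secondary nulls true, the chance of at least one nominally significant result in either direction is about 15–23% for five tests and 19–34% for eight, over correlations from 0.7 down to 0. At 0.9 it is about 10–12%. For false claims of benefit, the range is about 7% (five tests, correlation 0.7) to 18% (eight independent tests), against 2.5% for one test.

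The correlations are assumptions, and the upper ends are ceilings. The inflation matters only so far as secondary results are presented as confirmatory, which the plan neither states nor rules out. This should be corrected, but it does not threaten the primary conclusion.

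**What to change.** Add a paragraph to 8.2.3 that does four things:

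1. States the success criterion for the two primary outcomes in 3.1 (both required, or either with its own error control). The plan has no such rule, and a gate cannot be written without one.
2. States whether symptom absence is one test or four, which fixes the family at five or eight.
3. Tests the secondaries confirmatorily only if the primary criterion is met, with a named procedure that holds the secondary family at two-sided 0.05. Holm is one choice, with a first threshold of 0.05/5 = 0.01 or 0.05/8 = 0.00625. A fixed sequence in a stated order is another. Both hold the bound under any correlation.
4. Otherwise reports estimates with 95% confidence intervals, labelled exploratory. Giving all secondaries that label from the outset would also resolve the point.

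The text should be settled before unblinding. It needs no extra patients and leaves the primary analysis unchanged.

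The cost is a stricter threshold for individual secondary claims. The documents give no assumed sham rates for the secondaries, so their power cannot be computed. As an illustration only, take a comparison with the same rates as the primary (35.4% against 22.0%, 239 per group). Its power is Φ[(0.134·√239 − z·0.6397)/0.6327], where 0.6397 and 0.6327 are the two square roots in step 1 of the working. This gives 90% at 0.05 (z = 1.960), 75% at 0.01 (z = 2.576) and 69% at 0.00625 (z = 2.734). Those last two figures are for Holm's first step, and later steps are less strict. A fixed sequence keeps 0.05 at each step but stops at the first failure.
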